#### **4.3.2.4 Lenalidomide**

Lenalidomide will be administered orally once daily on Days 1–21 of Cycles 1–6 (28-day cycles) during induction treatment and on Days 1–21 of each month during consolidation or first 12 months of maintenance treatment. During the dose-escalation phase, lenalidomide will be administered at a dose of 10, 15, or 20 mg (dose may be de-escalated to 5 mg). During the expansion phase, lenalidomide will be administered at the RP2D during induction treatment and at 10 mg during consolidation or maintenance treatment.

Lenalidomide capsules should be swallowed whole with water and should not be broken, chewed, or opened. The capsules may be taken with or without food, except on lenalidomide PK sampling days (see [Appendix 3](#)), where the patient should fast (water

allowed) at least 2 hours before and at least 1 hour after the lenalidomide dose. On lenalidomide PK sampling visits, lenalidomide dose will be taken in the clinic.

Lenalidomide should be administered at approximately the same time each day. If a dose of lenalidomide is missed and it has been < 12 hours since the time of the scheduled dose, the patient may take the missed dose. If it has been > 12 hours, the dose should be skipped and the next dose should be taken at the regularly scheduled time. Two doses should not be taken at the same time. If a dose had been vomited, the dose should not be re-taken.

At each cycle, each patient will be supplied with only enough lenalidomide for that cycle. A drug diary will be provided to the patient to record oral administration of doses, including the date and time. Patients will be instructed to return empty bottles or unused capsules. The investigator is responsible for monitoring patient compliance by monitoring the patient diary and counting unused capsules.

#### **4.3.2.5 Premedication and Other Required Medication**

Lenalidomide increases the risk of thromboembolism. All patients will be required to take daily aspirin (75–100 mg) for TE prophylaxis during lenalidomide treatment and until 28 days after the last dose of lenalidomide. Patients who are unable to tolerate aspirin, patients with a history of TE, and patients at high risk of TE should receive warfarin or low-molecular-weight heparin (LMWH).

Patients should receive premedication as outlined in [Table 13](#).

**Table 13 Premedication**

Timepoint	Patients Requiring Premedication	Premedication	Administration
Cycle 1, Day 1	
 
All patients
 
	
 
Oral corticosteroida
 
	Complete ≥ 1 hour prior to obinutuzumab or rituximab infusion
	
 
All patients
 
	
 
Antihistamine drugb
 
Oral analgesic/antipyreticc
 
	Administer ≥ 30 minutes prior to obinutuzumab or rituximab infusion
	
 
Patients at risk for TLS (e.g., because of bulky disease or renal impairment [creatinine clearance < 70 mL/min])
 
	
 
Allopurinol or suitable alternative, such as rasburicase, along with adequate hydration
 
	Administer prior to obinutuzumab or rituximab infusion
Cycle 1, Days 8 and 15  Cycles 2 and Beyond, Day 1	
 
Patients with no IRR during the previous infusion
 
	
 
Oral analgesic/anti-pyreticc
 
	Administer at least 30 minutes prior to obinutuzumab infusion. For patients receiving rituximab, premedication may be omitted at the investigator's discretion.
	
 
Patients with Grade 1 or 2 IRR during the previous infusion
 
	
 
Antihistamine drugb
 
Oral analgesic/antipyreticc
 
	Administer ≥ 30 minutes prior to obinutuzumab or rituximab infusion
	
 
Patients with Grade 3 IRR, wheezing, urticarial, or other symptoms of anaphylaxis during the previous infusion
 
Patients with bulky disease
 
	
 
Oral corticosteroida
 
	Complete ≥ 1 hour prior to obinutuzumab or rituximab infusion
			
 
Antihistamine drugb
 
Oral analgesic/antipyreticc
 

	
 
Patients still at risk for TLS
 
	
 
Allopurinol or suitable alternative, such as rasburicase, along with adequate hydration
 
	Administer prior to obinutuzumab or rituximab infusion

IRR=infusion-related reaction; TLS=tumor lysis syndrome.

a Treat with 100 mg of prednisone or prednisolone, 20 mg of dexamethasone, or 80 mg of methylprednisolone. Hydrocortisone should not be used, as it has not been effective in reducing rates of IRR.

b For example, 50 mg of diphenhydramine.

c For example, 1000 mg of acetaminophen/paracetamol.

### **4.3.3 Investigational Medicinal Product Accountability**

All IMPs required for completion of this study (obinutuzumab, *rituximab*, polatuzumab vedotin, and lenalidomide) will be provided by the Sponsor. The study site will acknowledge receipt of IMPs using the IxRS to confirm the shipment condition and content. Any damaged shipments will be replaced. *Lenalidomide will be dispensed to sites in the United States via the Celgene REMS™ system. For sites outside the United States, lenalidomide will be dispensed to sites through the study IxRS. Sites will be trained on lenalidomide specific requirements by their study monitors.*

IMPs will either be disposed of at the study site according to the study site's institutional standard operating procedure or returned to the Sponsor with the appropriate documentation. The site's method of IMP destruction must be agreed to by the Sponsor. The site must obtain written authorization from the Sponsor before any IMP is destroyed, and IMP destruction must be documented on the appropriate form.

Accurate records of all IMPs received at, dispensed from, returned to, and disposed of by the study site should be recorded on the Drug Inventory Log.

### **4.3.4 Post-Trial Access to Obinutuzumab, Rituximab, Polatuzumab Vedotin, and Lenalidomide**

Currently, the Sponsor does not have any plans to provide obinutuzumab, *rituximab*, polatuzumab vedotin, or any other study treatments or interventions to patients who have completed the study. The Sponsor will evaluate whether to continue providing obinutuzumab, *rituximab*, or polatuzumab vedotin in accordance with the Roche Global Policy on Continued Access to Investigational Medicinal Product, available at the following Web site:

[http://www.roche.com/policy\\_continued\\_access\\_to\\_investigational\\_medicines.pdf](http://www.roche.com/policy_continued_access_to_investigational_medicines.pdf)

## **4.4 CONCOMITANT THERAPY**

Concomitant therapy includes any medication (e.g., prescription drugs, over-the-counter drugs, herbal or homeopathic remedies, nutritional supplements) used by a patient from 7 days prior to the screening period to the visit at EO1 or at the end of post-induction treatment, whichever occurs later. All such medications should be reported to the investigator and recorded on the Concomitant Medications eCRF.

### **4.4.1 Permitted Therapy**

TE prophylaxis treatment and premedication should be administered as described in Section 4.3.2.5.

Hematopoietic growth factors are allowed if clinically indicated and used in accordance with the prescribing information. G-CSF may be administered in each cycle of therapy as primary prophylaxis for neutropenia, per American Society of Clinical Oncology

(ASCO), EORTC, and European Society for Medical Oncology (ESMO) guidelines (Smith et al. 2006) or per each site's institutional standards.

Patients who use oral contraceptives, hormone-replacement therapy, or other maintenance therapy should continue their use. However, it must be noted that erythropoietic agents or other agents that may increase the risk of thrombosis, such as estrogen-containing therapies (e.g., oral contraceptives), should be used with caution, because of the increased risk of TE in patients taking lenalidomide. Suitable methods of contraception are presented in Section 4.1.1.

Patients using concomitant medication that could possibly worsen thrombocytopenia-related events (e.g., platelet inhibitors and anticoagulants) may be at greater risk of bleeding. When possible, replace prior vitamin K antagonist therapy with LMWH prior to Day 1 of Cycle 1.

Patients who are receiving digoxin should undergo periodic monitoring of digoxin plasma levels, in accordance with clinical judgment and based on standard clinical practice, because of potential drug interactions with lenalidomide.

Drug-drug interactions between warfarin and lenalidomide have been excluded. However, a close monitoring of PT and INR is recommended in patients receiving warfarin.

There is an increased risk of rhabdomyolysis when statins are administered with lenalidomide, which may be simply additive. Enhanced clinical and laboratory monitoring is warranted notably during the first weeks of treatment.

On the basis of simulations, unconjugated MMAE exposure following polatuzumab vedotin administration with CYP3A4 inhibitors or inducers is unlikely to be altered by more than 50%. Furthermore, MMAE is unlikely a perpetrator of drug interactions. The patients who receive strong CYP3A4 inhibitors or P-glycoprotein (P-gp) inhibitors in combination with polatuzumab vedotin will be closely monitored for adverse reactions if any.

Prophylactic treatment with antibiotics should be administered as per standard practice.

Necessary supportive measures for optimal medical care will be given throughout the study according to institutional standards.

#### **4.4.2 Prohibited Therapy**

Use of the following therapies (excluding protocol-specified treatments) is prohibited during the study:

- Any anti-cancer therapy, approved or investigational, other than intrathecal central nervous system prophylaxis
- Hormonal therapy other than contraceptives, stable hormone-replacement therapy, or megestrol acetate
- Biologic agents other than hematopoietic growth factors (as described in Section 4.4.1)
- *Vaccination with live vaccines is not recommended during treatment with obinutuzumab or rituximab and until B-cell recovery*

#### **4.5 STUDY ASSESSMENTS**

See [Appendix 1](#), [Appendix 2](#), and [Appendix 3](#) for the schedules of assessments performed during the study.

##### **4.5.1 Informed Consent Forms and Screening Log**

Written informed consent for participation in the study must be obtained before performing any study-related procedures. Informed Consent Forms for enrolled patients and for patients who are not subsequently enrolled will be maintained at the study site.

All screening evaluations must be completed and reviewed by the investigator to confirm that patients meet all eligibility criteria before enrollment. The investigator will maintain a screening log to record details of all patients screened and to confirm eligibility or record reasons for screening failure, as applicable.

Results of standard-of-care tests or examinations performed prior to obtaining informed consent, and within the defined window, may be used as screening and baseline assessments (see [Appendix 1](#) and [Appendix 2](#)); such tests do not need to be repeated for screening purposes (e.g., screening tumor assessment).

Study treatment should be initiated within 28 days after the Informed Consent Form has been signed.

##### **4.5.2 Medical History and Demographic Data**

Medical history includes clinically significant diseases, surgeries, reproductive status, smoking history, and alcohol and drug abuse. In addition, all medications (e.g., prescription drugs, over-the-counter drugs, herbal or homeopathic remedies, nutritional supplements) used by the patient within 7 days prior to the screening period will be recorded.

Demographic data will include age, sex, and self-reported race/ethnicity.

The following clinical parameters relative to disease history, diagnosis, and prognostic indices will be recorded at screening:

- Date of initial diagnosis
- ECOG Performance Status (see [Appendix 6](#))
- Ann Arbor staging (see [Appendix 9](#))
- For patients with FL: Follicular Lymphoma International Prognostic Index (FLIPI) and Follicular Lymphoma International Prognostic Index 2 (FLIPI2) (see [Appendix 10](#))
- For patients with DLBCL: IPI (see [Appendix 10](#))
- B symptoms (unexplained fever >38°C, night sweats, and unexplained weight loss >10% of body weight over 6 months)
- Previous lines of anti-lymphoma treatment and response to prior therapy, date of disease progression in relation to start date of prior therapy, and date of last dose of prior therapy

#### **4.5.3 Physical Examinations**

A complete physical examination should be performed at screening and should include an evaluation of the head, eyes, ears, nose, and throat, and the cardiovascular, dermatological, musculoskeletal, respiratory, gastrointestinal, genitourinary, and neurological systems. Any abnormality identified at baseline should be recorded on the General Medical History and Baseline Conditions eCRF. Height and weight will be recorded.

As part of tumor assessment, the physical examination should include evaluation for the presence of enlarged nodes, palpable hepatomegaly, and splenomegaly. This information will be recorded on the appropriate Tumor Assessment eCRF.

At subsequent visits (or as clinically indicated), targeted (limited, symptom-directed) physical examinations should be performed. Targeted physical examinations should be limited to systems of primary relevance (e.g., cardiovascular and respiratory systems), systems associated with symptoms (newly emergent or monitored from baseline), and areas associated with tumor assessment (lymph nodes, liver, spleen, and any other areas identified at baseline) (see Section [4.5.5](#)).

Changes from baseline abnormalities should be recorded in patient notes. New or worsened clinically significant abnormalities should be recorded as adverse events on the Adverse Event eCRF.

#### **4.5.4 Vital Signs**

Vital signs will include measurements of respiratory rate, pulse rate, body temperature, and systolic and diastolic blood pressures while the patient is in a seated position. Vital sign measurements will be performed as outlined in the schedules of assessments

(see [Appendix 1](#) and [Appendix 2](#)), but the associated data, other than the data collected at screening, do not need to be recorded on the eCRF (except in the case of an adverse event).

#### **4.5.5 Tumor and Response Evaluations**

All evaluable or measurable disease must be documented at screening and re-assessed at each subsequent tumor evaluation. Response will be assessed by the IRC and the investigator on the basis of PET and CT scans, using the Lugano 2014 criteria, *taking into account results of bone marrow examinations for patients with bone marrow involvement at screening*.

In this study, the Lugano 2014 criteria for a PET-CT–based CR have been slightly modified to require normal bone marrow for patients with bone marrow involvement at screening. *Additionally, designation of PET-CT-based PR requires that CT-based response criteria for a CR or PR be met in addition to the PET-CT-based response criteria for a PR* (see [Appendix 5](#)).

##### **4.5.5.1 Radiographic Assessments**

PET scans should include the base of the skull to mid-thigh region. Full body PET scans should be performed when clinically appropriate.

CT scans with oral and IV contrast should include chest, abdomen, and pelvic scans. CT scans of the neck should be included if clinically indicated (i.e., if evidence of disease upon physical examination) and must be repeated throughout the study if there is disease involvement at baseline.

PET-CT scans and diagnostic CT scans should be acquired according to a standardized imaging manual, which will be provided to all sites.

If contrast is medically contraindicated (e.g., patients with contrast allergy or impaired renal clearance), MRI scans of the chest, abdomen, and pelvis (and neck, if clinically indicated) and a non-contrast CT scan of the chest may be performed. If MRI scans cannot be obtained, CT scans without contrast are permitted as long as this allows consistent and precise measurement of the targeted lesions during the study treatment period.

The same radiographic assessment modality must be used for all response evaluations to ensure consistency across different timepoints (including unscheduled assessments).

A full tumor assessment, including radiographic assessment, must be performed any time disease progression or relapse is suspected.

Additional details regarding imaging procedures will be provided in the Imaging Manual.

#### **4.5.5.2 Bone Marrow Assessments**

Bone marrow examinations are required at screening for staging purposes in all patients and should be performed within approximately 3 months prior to Day 1 of Cycle 1.

If bone marrow infiltration is present at screening, a bone marrow biopsy is required at the EOI response assessment for all patients who may have achieved a CR. In patients with a PR and continued bone marrow involvement, a subsequent bone marrow examination may be required to confirm a CR at a later timepoint.

Any additional (unscheduled) bone marrow examinations performed during the study will be at the discretion of the investigator.

#### **4.5.6 Laboratory, Biomarker, and Other Biological Samples**

##### **Local Laboratory Assessments**

Samples for the following laboratory tests will be analyzed at the study site's local laboratory for analysis:

- Hematology: hemoglobin, hematocrit, platelet count, RBC count, WBC count, and percent or absolute WBC differential count (neutrophils, eosinophils, basophils, monocytes, lymphocytes, other cells)
- Chemistry panel (serum or plasma): sodium, potassium, glucose, BUN or urea, creatinine, calculated creatinine clearance, calcium, total bilirubin, direct bilirubin, total protein, albumin, ALT, AST, alkaline phosphatase, LDH, uric acid, glycosylated hemoglobin (HbA1c), amylase, and lipase (amylase and lipase only during induction). HbA1c will be measured only at Screening and can be obtained in a non-fasting state.
- *Thyroid-stimulating hormone, triiodothyronine, thyroxine*
- $\beta_2$  microglobulin
- Coagulation: INR, aPTT (or PTT), and PT
- Pregnancy test

All women of childbearing potential must have two negative serum pregnancy test results (minimum sensitivity, 25 mIU/mL) prior to initiating therapy: at 10–14 days prior to Day 1 of Cycle 1 and within 24 hours prior to Day 1 of Cycle 1. Urine pregnancy tests will be performed at specified subsequent visits (see [Appendix 1](#) and [Appendix 2](#)). If a urine pregnancy test is positive, it must be confirmed by a serum pregnancy test.

- Viral serology
  - Hepatitis B testing includes HBsAg and total HBcAb
  - Hepatitis C testing includes HCV antibody
  - HIV testing (if required per local regulatory requirements)
- Quantitative immunoglobulins: IgA, IgG, and IgM

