##### **3.1.2.1.1**      **Definition of Dose-Limiting Toxicity**

In this study, a DLT is defined as any one of the following events occurring during the first cycle of treatment and assessed by the investigator as related to study treatment *that is not attributed to disease progression or another clearly identified cause:*

- *Any adverse* event of any grade that leads to a delay of > 14 days in the start of the next treatment cycle
- *Any* Grade 3 or 4 non-hematologic adverse event, with the following exceptions:
  - Grade 3 or 4 IRRs

Note that IRRs may occur even after a small amount of drug has been administered (i.e., IRRs are not dose dependent).

- Grade 3 diarrhea that responds to therapy within 72 hours
- Grade 3 nausea or vomiting that occurs in the absence of premedication and responds to adequate therapy within 72 hours
- *Grade 3 laboratory TLS without manifestations of clinical TLS (i.e., creatinine  $\geq 1.5 \times$  upper limit of normal (ULN) and/or renal dysfunction, cardiac arrhythmias, seizures, or sudden death) that resolves within 7 days (see [Appendix 12](#))*
- *Grade 3 fatigue that resolves to Grade  $\leq 2$  within 7 days*
- *Grade 3 laboratory abnormality that is asymptomatic and deemed by the investigator not to be clinically significant*
- *Grade 3 elevation in ALT or AST, provided the following criteria are met:*
  - ALT or AST level is no greater than  $8 \times$  ULN*
  - ALT or AST elevation resolves to Grade  $< 2$  ( $< 5$  ULN) within 7 days*
  - Total and direct bilirubin and other laboratory parameters of liver synthetic function (e.g., prothrombin time) are normal*
  - No clinical signs or symptoms of hepatic injury*
- *Any increase in hepatic transaminase  $> 3 \times$  baseline AND an increase in direct bilirubin  $> 2 \times$  ULN, WITHOUT any findings of cholestasis or jaundice or signs of hepatic dysfunction AND in the absence of other contributory factors (e.g., worsening of metastatic disease or concomitant exposure to known hepatotoxic agent or of a documented infectious etiology) is suggestive of potential drug-induced liver injury (according to Hy's Law) and will be considered a DLT.*
- *In patients with Grade 1 ALT or AST elevation at baseline as a result of liver metastases, only a Grade  $\geq 3$  elevation that is also  $\geq 3 \times$  baseline lasting  $> 7$  days will be considered a DLT.*
- Hematologic adverse event that meets any of the following criteria:

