### **5.2.3 Adverse Events of Special Interest (Immediately Reportable to the Sponsor)**

Adverse events of special interest are required to be reported by the investigator to the Sponsor immediately (i.e., no more than 24 hours after learning of the event; see Section 5.4.2 for reporting instructions). Adverse events of special interest for this study include the following:

- Cases of potential drug-induced liver injury that include an elevated ALT or AST in combination with either an elevated bilirubin or clinical jaundice, as defined by Hy's law (see Section 5.3.5.7)
- Suspected transmission of an infectious agent by the study treatment, as defined below:

Any organism, virus, or infectious particle (e.g., prion protein transmitting transmissible spongiform encephalopathy), pathogenic or non-pathogenic, is considered an infectious agent. A transmission of an infectious agent may be suspected from clinical symptoms or laboratory findings that indicate an infection in a patient exposed to a medicinal product. This term applies only when a contamination of any of the study treatment components is suspected.
- TLS of any grade, irrespective of causality
- *Second malignancies*

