## Appendix 2 Schedule of Assessments for Patients with Diffuse Large B-Cell Lymphoma

	Screening a		Induction (6 months; 28-day cycles)								EOI	Consolidation (6 months)		EOC b	Post- Treatment FU Period (Q3M) d	Survival FU Period (Q3M) d
	D -28 to D -1	D -14 to D -1	Cycle 1 (±1 day)				Cycles 2-6 (±2 days)				After Last Induction Dose c	Monthly (±3 days)	Every 2 months (±1 wk)	35 Days after Last Dose		
			D1	D8	D15	D22	D1	D8	D15	D22						
Informed consent e	x															
Demographic data	x															
Medical history	x															
ECOG Performance Status	x															
Vital signs f	x		x				x					x		x		
Height	x															
Weight	x		x				x									
12-lead ECG	x										x g			x		
Complete physical examination h,i	x															
Targeted physical examination ij							D1, Cycles 2 and 4				x		x	x	x	
Ann Arbor and IPI	x															
B symptoms	x															
β 2 microglobulin			x													
Hematology k		x	x l,m	x m	x m	x m	x m	x m,n	x m,n	x m,n	x g	x m		x	x	
Chemistry panel (serum or plasma) o		x	x l,m		x m		x m		x m,n		x g	x m		x	x	
TSH, T3, T4	x		Every 3 months													

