### Schedule of Assessments for Patients with Diffuse Large B-Cell Lymphoma (cont.)

---

- k Includes hemoglobin, hematocrit, platelet count, RBC count, WBC count, and percent or absolute WBC differential count (neutrophils, eosinophils, basophils, monocytes, lymphocytes, other cells).
- l Screening laboratory assessments may be used for Day 1 of Cycle 1 if performed within 72 hours prior to Day 1 of Cycle 1.
- m Perform hematology and chemistry tests within 72 hours prior to Day 1 of each cycle during induction or each month during consolidation, and within 24 hours prior to other timepoints during induction treatment. *CBC to be monitored every week during first 8 weeks of lenalidomide therapy.* Samples for exploratory biomarker research should be collected at the same time as hematology and chemistry samples. *For  $\beta$ 2 microglobulin and Quantitative IgA, IgG, IgM: C1D1 requires predose collection.* For plasma cytokine analysis: C1D1 requires predose collection and 2-hour post-dose collection. All other timepoints thereafter will be predose.
- n Cycles 2 and 3 only.
- o Includes sodium, potassium, glucose, BUN or urea, creatinine, calculated creatinine clearance, calcium, total bilirubin, direct bilirubin, total protein, albumin, ALT, AST, alkaline phosphatase, amylase, lipase, LDH, and uric acid (amylase and lipase only during induction).
- p All women of childbearing potential will have two negative serum pregnancy test results prior to initiating treatment: at 10–14 days prior to Day 1 of Cycle 1 and within 24 hours prior to Day 1 of Cycle 1. Urine pregnancy tests are required after treatment initiation (including times of treatment interruption) as follows: every week during the first cycle and then every 4 weeks during treatment for women with regular menstrual cycles or every 2 weeks during treatment for women with irregular menstrual cycles, any time the patient misses her period or has unusual menstrual bleeding, at the time of treatment discontinuation, and at *Days 14 and 28 following* the last dose of study treatment. If a urine pregnancy test is positive, it must be confirmed by a serum pregnancy test.
- q Includes hepatitis B surface antigen, total hepatitis B core antibody, and hepatitis C virus antibody. HIV test should also be performed if required by local regulatory requirements.
- r See [Appendix 4](#) for detailed PK collection schedule.

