### Diagnostic Criteria for Tumor Lysis Syndrome

	Lab Value Threshold	
Lab Changes	Uric acid	$\geq 476 \mu\text{mol/L}$ (8 mg/dL)
	Potassium	$\geq 6\text{mmol/L}$ (6 mEq/L)
	Phosphorus	$\geq 1.45 \text{mmol/L}$ (4.5 mg/dL)
	Calcium	$\leq 1.75 \text{mmol/L}$ (7 mg/dL)
Cairo-Bishop Definition	2 or more of above lab changes or if change is more than 25% from baseline	Laboratory TLS
	Occurs within 3 days before or 7 days after therapy Laboratory TLS accompanied by cardiac arrhythmia, sudden death, seizure, or acute renal failure (serum creatinine <math>\geq 1.5 \times \text{ULN}</math>)	Clinical TLS
Howard Definition (in addition to Cairo-Bishop definition)	2 or more above lab changes occur simultaneously	Laboratory TLS
	25% change is not a criteria Symptomatic hypocalcemia	Clinical TLS

*TLS = Tumor Lysis Syndrome; ULN = upper limit of normal.*

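### Phosphorus, one of the four laboratory TLS analytes, is not in the required chemistry panel, and DLBCL patients have no scheduled chemistry in the week after first dose

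*Combined protocol and SAP*

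**What the plan says.** **Status of TLS.** Section 5.2.3 names "TLS of any grade, irrespective of causality" as an adverse event of special interest (AESI). The same section states that "Adverse events of special interest are required to be reported by the investigator to the Sponsor immediately", with a 24-hour limit. Section 5.2.5 also lists TLS as a selected adverse event and keeps it immediately reportable when it is not serious. Under Section 6.5, AESIs and selected adverse events are summarized and listed.

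**DLT exception.** Section 3.1.2.1.1 does not count as a DLT "Grade 3 laboratory TLS without manifestations of clinical TLS" that clears within 7 days, and points to Appendix 12. Section 3.1.3.1 applies the same DLT criteria to the DLBCL escalation.

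**Definition.** Appendix 12 gives thresholds for uric acid, potassium, phosphorus and calcium. Under the first of its two definitions, laboratory TLS is "2 or more of above lab changes or if change is more than 25% from baseline", with the timing "Occurs within 3 days before or 7 days after therapy". The second definition uses the same four analytes, asks that the changes be simultaneous, and drops the 25% criterion.

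**Panel.** Section 4.5.6 lists, among other tests, "creatinine, calculated creatinine clearance, calcium, total bilirubin, direct bilirubin, total protein, albumin, ALT, AST, alkaline phosphatase, LDH, uric acid". Footnote o of Appendix 2 opens "Includes sodium, potassium, glucose, BUN or urea, creatinine, calculated creatinine clearance, calcium" and continues with a matching list. Footnote o of Appendix 1 does the same.

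**Schedule.** In Appendix 2 (DLBCL), chemistry in Cycle 1 is marked on Days 1 and 15. In Appendix 1 (FL) it is marked on Days 1, 8 and 15.

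**The concern.** Laboratory TLS is found by blood tests, so what the protocol requires to be measured, and when, determines what can be counted. Here the definition and the required measurements do not match. One of the four defining analytes is in no panel list, and one of the two histologies has no required panel in the week after first dose.

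Two outputs are affected. The first is the AESI count: an event that nobody looked for enters the summaries as no event, and a difference between FL and DLBCL could partly reflect the testing schedule. The second is dose escalation, where laboratory TLS has its own exception and cohorts hold 3 to 6 patients.

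The mismatch looks like an oversight of Version 2. That amendment added Appendix 12 and the laboratory TLS exception. It also extended the Section 4.5.6 laboratory list with thyroid tests, but not with phosphorus. No rationale is given for the omission or for the difference between the two schedules.

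**Working it through.** The plan gives no figure to reproduce. The check sets the definition against the panel lists and the schedules.

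**1. Analytes**

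| Appendix 12 analyte | Section 4.5.6 | App. 1, footnote o | App. 2, footnote o |
|---|---|---|---|
| Uric acid | yes | yes | yes |
| Potassium | yes | yes | yes |
| Calcium | yes | yes | yes |
| Phosphorus | no | no | no |

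Since phosphorus is absent from the panel, it is also absent at screening. Even an unscheduled later value may then have no baseline for the 25% criterion.

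**2. Combinations that can qualify.** Two of four analytes give C(4,2) = 6 pairs. Three contain phosphorus (phosphorus with each of the other three), and three do not, C(3,2) = 3. Required tests can show the second three only. A patient with phosphorus and two other abnormalities is still identified. The patient missed is the one whose only two qualifying changes include phosphorus.

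**3. Cycle 1 chemistry by visit**

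| | Day 1 | Day 8 | Day 15 | Day 22 |
|---|---|---|---|---|
| FL chemistry (App. 1) | yes | yes | yes | no |
| DLBCL chemistry (App. 2) | yes | no | yes | no |
| DLBCL hematology (App. 2) | yes | yes | yes | yes |

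The Day 1 draw is a pre-dose draw: footnote m allows it up to 72 hours before, and the notes to Appendix 2 place assessments on treatment days before dosing.

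**4. Timing after the first dose.** Cycle 1 visits carry ±1 day, and footnote m allows draws at other induction timepoints up to 24 hours before the visit.

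- Day 15, nominal 15 − 1 = 14 days after Day 1: earliest 14 − 1 − 1 = 12, latest 14 + 1 = 15.
- Day 8 (FL), nominal 8 − 1 = 7 days: earliest 7 − 1 − 1 = 5, latest 7 + 1 = 8.

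Required post-dose panels planned for the 7 days after first dose: DLBCL 0, FL 1.

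**5. Patients affected by the timing gap.** Section 3.1.3.1 plans 12–18 DLBCL escalation patients and Section 3.1.3.2 about 40 in expansion: 12 + 40 = 52 to 18 + 40 = 58. The missing analyte affects both histologies.

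**6. DLT calls.** Grade 3 laboratory TLS without clinical TLS that clears within 7 days is not a DLT in any case. What could be missed is an event outside the exception. One that starts soon after the first dose and lasts just beyond 7 days could be over before the earliest Day 15 draw, at 12 days.

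**The case against.** The strongest case on the other side is that the gap is narrower than it looks.

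- *Later DLBCL panels exist.* Chemistry is scheduled on Cycle 1 Day 15, Day 1 of Cycles 2–6 and Day 15 of Cycles 2 and 3, and any two of the three measured analytes suffice. Appendix 12 speaks of therapy, not of the first dose. Lenalidomide runs on Days 1–21, so the Day 15 sample lies within 7 days of a dose. This stands. A reader might infer that laboratory TLS in DLBCL can be found only by unscheduled testing; the schedule does not support that. Only the claim about the 7 days after first dose survives.
- *Pair counts are not case counts.* This stands too. A reader might take 3 of 6 pairs to mean that half of cases are missed. That would need the pairs to be equally likely, and nothing in the documents says so.
- *DLT calls are largely protected.* The exception already removes Grade 3 laboratory TLS that clears within 7 days, and a separate one removes asymptomatic Grade 3 laboratory abnormalities judged not clinically significant. Once an event is found, Table 19 ties resumption of treatment to complete resolution, and Section 5.5.1 requires follow-up of every adverse event. Whether a detected event cleared in 7 days therefore does not hang on the next scheduled panel. This stands for detected events; it does nothing for undetected ones.
- *Other safeguards.* Section 5.1.4.6 asks for close monitoring of patients with high tumor burden, Table 13 provides prophylaxis, and nothing bars extra tests. True, but these provisions name no analytes and no times for testing, so ascertainment rests on local practice.
- *The definition is open to reading.* In the table as extracted, the 3-day and 7-day limits stand in the row for clinical TLS, and Section 5.2.3 says TLS without saying laboratory TLS. The phosphorus gap does not depend on the time limits. That the AESI covers laboratory TLS is a reading, supported by Appendix 12 and the DLT exception, which both treat it as a form of TLS.
- *FL Day 8 is an obinutuzumab day.* That may explain the FL panel, but rituximab and polatuzumab vedotin are not given on Day 15 of Cycle 1, and DLBCL chemistry is marked there.

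**Conclusion.** The point holds in a limited form. Required tests cover three of the four Appendix 12 analytes, so laboratory TLS whose only two qualifying changes include phosphorus cannot be identified from them in either histology. For about 52–58 DLBCL patients no required post-dose chemistry falls in the 7 days after first dose, against one panel in FL. Early laboratory TLS in DLBCL therefore depends on unscheduled testing. Ascertainment of an immediately reportable event, and of events considered under the laboratory TLS exception, is incomplete and unequal between histologies.

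The number of missed cases cannot be estimated from the documents. A reader might also infer that escalation decisions are seriously compromised, or that every component carries an established TLS risk. Neither is supported. The effect on DLT calls is small for the reasons above, and Section 5.1.5 calls the polatuzumab vedotin risk theoretical.

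The conclusion assumes that the AESI includes laboratory TLS and, for the timing part, that the week after first dose is a period of interest. The primary efficacy endpoint is unaffected. This should be fixed, but the trial's main inference does not turn on it.

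**What to change.** Reconcile Appendix 12, Section 4.5.6 and the two schedules:

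1. Add phosphorus to the chemistry panel in Section 4.5.6 and in footnote o of Appendices 1 and 2, screening included, so that a baseline exists for the 25% criterion.
2. Mark chemistry on Cycle 1 Day 8 in Appendix 2, as in Appendix 1. DLBCL patients already have hematology on that day (Appendix 2) and a polatuzumab vedotin MMAE sample (Appendix 4), so no visit is added and the existing draw can be used.
3. State the limit of step 2. With windows, a Day 8 sample falls about 5 to 8 days after Day 1, at the edge of the 7-day period and sometimes just outside it. It aligns DLBCL with FL without covering the whole week.

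The cost is one more analyte per chemistry draw, one more DLBCL panel, and probably a few more asymptomatic laboratory TLS cases reported as AESIs. The change concerns data collection only; no dose or treatment rule is altered.
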